**Tetrasodium EDTA central venous catheter lock solution in home
parenteral nutrition patients: ease of use and cost analysis**

**Written by
[name] MD**

Principal Investigator: [name], FRCPC

**Department of Gastroenterology
Toronto General Hospital**

Abstract:

Parenteral nutrition (PN) is a lifesaving therapy in patients with chronic intestinal failure. PN is administered via a central venous catheter (CVC), and patients are dependent on this line for ongoing nutrition. However, the presence of a CVC is associated with a risk of thrombosis and bloodstream infection. Many different types of catheter lock solutions have been used to mitigate these risks. They include solutions primarily aimed at reducing thrombosis, such as heparin and citrate, and others primarily aimed at reducing infection such as ethanol and antibiotics (for example, taurolidine). One recently developed solution, tetrasodium EDTA, aims to reduce both thrombosis and infection. This scientific review provides an overview of central venous catheter lock solutions, and an ease-of-use and cost analysis comparing heparin and tetrasodium EDTA in one home parenteral nutrition program in Toronto, Canada.

Keywords: parenteral nutrition, central venous catheter, heparin, taurolidine, citrate, ethanol, tetrasodium EDTA

Background:

Parenteral nutrition (PN) is a life-sustaining therapy required in patients who do not have a functioning gastrointestinal tract. This can be either second to surgical removal, or malfunction (such as in malabsorptive conditions and dysmotility). The intravenous provision of nutrition requires central venous access where a hyperosmolar nutrient solution can be infused. A variety of central venous catheters (CVCs) can be used, including peripherally inserted central catheters (PICC), tunneled catheters and implanted ports. The most common complication, and most frequent cause of hospitalization in patients on home PN is bloodstream infection. (8)

There are several new devices or solutions that are being developed to be used as primary prophylaxis for CRBSI. These include catheters with antibacterial and/or anti-biofilm properties and different catheter lock solutions. Antibiotic lock solutions have been used for salvage of central venous catheters in confirmed CRBSI (1). However, it is not recommended as a primary prophylaxis due to the creation of resistant organisms. (2) According to the United States Center for Disease Control (CDC), antibiotics 'should be used only to manage infection.' (3) However, one antimicrobial solution, taurolidine, has not been found to promote the emergence of resistant bacterial strains and it has been used successfully as a lock solution to prevent CRBSI. Although an antibiotic may have anti-biofilm properties in high concentrations but it does not have anticoagulant properties. Ethanol lock solutions (varying concentrations, but usually 70%) have also been used successfully to reduce CRBSI, however, there have been adverse events when they are used in polyurethane lines and it does not inherently have anticoagulant properties. Historically, citrate lock solution has also been used to maintain catheter patency, but in a meta-analysis, there was no difference between heparin and citrate lock with regards to catheter thrombosis or catheter related bloodstream infection (12).

Although its use has been evaluated in hemodialysis catheters, there are no known studies examining the use of a tetra-sodium EDTA catheter lock solution in central venous catheters of patients on home PN.

Although both hemodialysis and home PN require central venous catheters, there are many differences inherent to the different usages. First, the types of catheters that are used can differ. There is more variety in the types of catheters used for home PN. Second, most patients undergo hemodialysis on a fixed schedule, three times per week for 4 to 8 hours each time, and, for the majority of patients, this is done in-center, with the assistance of a nurse. On the other hand, home PN is usually administered five or more days per week, at home, over 12 or more hours. It can be either administered with the assistance of a home care nurse or by the patient and/or their family/partner. Furthermore, the substance infused through the catheter is different. Specifically, amino acids and fat emulsions are usually only infused in home PN, although electrolytes and fluids can be infused in both.

Kitelock™, 4% tetrasodium EDTA catheter lock solution is the sole product of SterileCare Inc, a private medical devices and equipment company registered federally in Canada, and based in Markham, Ontario. Kitelock™ is licensed as a medical device, class 2 (license #96962, issue date 2016-05-10), by Health Canada.

RESEARCH DESIGN AND METHODS

The primary objective of this study is to evaluate patient acceptability of tetrasodium EDTA catheter lock solution in home parenteral nutrition patients.

The secondary aims are to evaluate: side effects, time for preparation and injection, cost and patient satisfaction.

This is a prospective, open-label, single-center study of the patient acceptability of using tetrasodium EDTA catheter lock solution in home parenteral nutrition patients. At study baseline, all patients will be on normal saline/heparin lock solution (which they receive normally as current standard of care) for at least 1 month before starting the study, as per inclusion criteria.

Patients will then start with one month (30 days) of their usual heparin and saline flush followed by one month (30 days) of tetrasodium EDTA solution with withdrawal (when possible), followed by one month (30 days) of tetrasodium EDTA solution. During the last week of each of the aforementioned three months, the patients will be asked to evaluate the lock and flush. Patients will be followed and treated according to usual care during the study, except for the catheter lock solution.

All patients receiving HPN at Toronto General Hospital will be invited to participate in the study. Patients will be recruited at their usually scheduled HPN appointment or by telephone. Consent will be taken by clinical fellow and nurse coordinator. Patients will be instructed on the use of the new lock solution via (1) telephone by the home TPN nurse. The patient or the other person administering the lock solution (usually caregiver or community nurse) will be responsible for filling the provided survey three times: once at the end of each month. The patients will be responsible for filling a data collection form with time of procedure, and any symptoms or side effects as they occur. The patient will receive four phone calls from the home TPN nurse in regards to this study: once at the beginning of the study and once at the end of each month. At each phone visit, the nurse will record the time to perform and any symptoms or side effects that the patient has written down in their data collection form, and administer the survey, in addition to inquiring about any interim events such as hospitalization, surgery and illness (at phone calls

2, 3 and 4) and compliance. The catheter lock solution will be distributed by Ontario Medical Supply, with home TPN solution and supplies, as per the patient's usual delivery schedule. Regular home TPN monitoring labs will be drawn at least once at the beginning of the study and once at the end of the study (3 months later), or more frequently, as clinically indicated or as per the patient's usual care.

SAMPLE SIZE

This is a pilot study; we plan to recruit 20 participants.

INCLUSION CRITERIA

Subjects who meet all of the following criteria can be enrolled in this study:

- Adult over the age of 18
- Both males and females
- Clinically stable for at least 4 weeks with no acute medical co-morbidities

EXCLUSION CRITERIA

- Inability to give informed consent
- Alcohol or drug abuse
- Pregnant and lactating women
- Clinical instability such as the following:
 - Acute pulmonary edema
 - Decompensated heart failure
 - Decompensated chronic liver disease
 - Severe post-traumatic conditions
 - Uncontrolled diabetes mellitus
 - Acute myocardial infarction
 - Acute stroke
 - Acute thromboembolism
 - Metabolic acidosis
 - Sepsis
 - Hypotonic dehydration
 - Coagulopathy with prolonged aPTT or INR
 - Unstable oncology patient
- Subjects who are hypersensitive or allergic to the product ingredients of tetrasodium EDTA
- Active therapy with long-term anti-microbial, such as taurolidine (not including patients receiving intermittent antimicrobial treatment for small intestinal bacterial overgrowth)
- Active participation in another home TPN clinical trial which may interfere with the results

HPN administration:

The patients are already part of the HPN program for **at least 1 month** (the minimum time on stable HPN as part of the inclusion criteria). These patients are familiar with self-administration of HPN. The

different lock solution will affect their usual practice and does require additional training/instructions due to the need to prepare the solution from a vial, injecting the line with the solution and withdraw the solution from the line

Lock procedures:

- 1) Heparin and saline (standard of care), as per protocol
- 2) Tetrasodium EDTA lock and withdraw
- 3) Tetrasodium EDTA lock and flush through

Prior to disconnecting PN tubing (when infusion complete):

- 1) Clean work area.
- 2) Gather: pre-filled 10 ml saline syringe; alcohol swabs; 3 ml or 5 ml empty syringe (depending on the type of line: 3mL for PICC and Hickman and 5mL for a Port-A-Cath); and Tetrasodium EDTA lock vial or Heparin pre-filled syringe (3 ml or 5 ml)
- 3) Wash your hands.
- 4) Swab end cap properly with alcohol swab before attaching any syringes. Open clamp.
- 5) **For Heparin lock:**
 - a. Flush catheter with pre-filled saline syringe as per usual routine.
 - b. Flush and lock catheter with pre-filled heparin syringe as per usual routine.
- 6) **For Tetrasodium EDTA:**
 - a. Draw up 3 ml or 5 ml Tetrasodium EDTA solution in empty syringe. Set aside.
 - b. Flush catheter with pre-filled saline syringe as per usual routine.
 - c. Flush and lock catheter with Tetrasodium EDTA solution (3 or 5 ml).
- 7) Close clamp.

Prior to connecting to PN tubing:

- 1) Clean work area.
- 2) Gather: prefilled 10 ml saline syringe; alcohol swabs; 3 ml or 5 ml empty syringe
- 3) Wash hands.
- 4) Swab end cap properly with alcohol swab before attaching any syringes as usual. Open clamp.
- 5) Attach empty syringe to the catheter.
- 6) Pull back 3 ml (or 5 ml) Tetrasodium EDTA lock solution from the catheter. It will be mixed with some blood, this is normal. Remove the syringe.
- 7) Swab end cap properly with alcohol again.
- 8) Flush catheter with 10 mL saline syringe as per routine.
- 9) Connect to PN tubing as per routine.
- 10) Start infusion as per routine.

If flushing Tetrasodium EDTA lock solution through the catheter, repeat above steps but omit 5 - 7.

Cost analysis (this is an estimate which may be modified after the trial):

Type	Solution	Dispensing fee	SAP application	Distribution	Supplies*	Education
Saline/heparin	\$2/use	0	N/A	0/contract	0/contract	0
Tetrasodium EDTA	\$3.50/use	0	N/A	0/contract	10ml syringe without needle	0.5h (\$40/hr)
Saline/taurolidine	\$20/10ml	\$11,99	2h (\$55/h) Per patient		3-5ml syringe with needle	0.5h (\$40/hr)

Measures:

1. Patient acceptability

See Form 2 below

2. Patient satisfaction

See Form 2 below

3. Time to prepare tetrasodium EDTA catheter lock solution

(1) From starting to prepare to infuse TPN to starting the TPN infusion (form 1)

(2) From disconnecting TPN tubing to completing catheter lock solution (form 1)

4. Symptoms and side effects

See Form 1: patient data collection form

5. Labs

Regular TPN labs, as per usual care, at the beginning and end of the study (form 4)

(1) Within 30 days of starting the study

(2) On, or up to 10 days after the last day of using the tetrasodium EDTA lock solution

Data collection forms:

-Form 1: patient data collection form:

-Record symptoms and side effects as they occur

-Record the time of the procedure on the first and last Monday of each 30-day period

-Form 2: survey on ease of use (3 per patient)

- to be filled by person administering the lock (RN, patient, family member), where possible

- to be filled three times, during the phone visit at the end of each month

- Form 3: Education time

-Nurse: over the phone

-Patient demonstration

Clinic Visits:

Clinic visits: None required

Follow up Phone call:

Each phone call will last for around 40 minutes. All participants will receive phone call at baseline and at the end of month 1,2 and 3.

Phone visits:

- (1) At baseline, prior to initiation of the product
- (2) At the end of month 1 (on days 27 to 30)
- (3) At the end of month 2 (on days 57 to 60)
- (4) At the end of month 3 (on days 87 to 90)

Follow-up phone call for the following purpose:

- **Safety:** by asking questions about side effects and tolerance to tetrasodium EDTA solution (from patient data collection form)
- **Compliance:** Recording the number of catheter lock solutions used.
- **Record times of procedure** (from patient data collection form)
- **Record events** (hospitalizations, antibiotics used, or interruption of lock solution use)
- **Record who is doing the flush** (nurse, patient or family member)
- **Perform a phone survey**
- Review the instructions** for the next month

SUBJECT WITHDRAWAL CRITERIA

In accordance with the Declaration of Helsinki, subjects are free to stop the study at any time for any or no reason, and without prejudice to further treatment. For subjects who decide to withdraw, effort would be made to contact him/her, to obtain information about the reason for discontinuation and any adverse events (AEs). All subjects who discontinue prematurely will be evaluated for AEs that are not resolved at the time of study discontinuation and will be followed for up to 4 weeks from the date the subject stops tetrasodium EDTA or as long as is medically relevant as judged by the principle investigator. All subjects who will withdraw from the study will be maintained on appropriated standard medical care. Subjects, who decide to be discontinued, will not be replaced.

Procedures to be taken in case of an adverse event (AE):

Patients receiving PN are complex and frequently have adverse events or complications that may be related to either their PN, their underlying disease or a medical/surgical procedures. Therefore, it is

expected that during the study, some HPN patients will have some AE that are most likely not related to the tetrasodium EDTA but more to HPN overall or underlying medical/surgical conditions.

If an AE occurs:

- 1- The HPN team will assess whether the AE is related or not to tetrasodium EDTA solution. Depending on the nature of the AE, tetrasodium EDTA solution may be put on hold based on standard medical practice.
- 2- If a line infection develops, it is general practice to hold HPN for 24-48 hours while antibiotics are started. HPN can be on hold longer if a central line needs to be changed, either as a result of certain types of line infections (eg. fungi, staph aureus) or because of line malfunctions. Generally all patients are expected to resume HPN within 1 week because, otherwise, they cannot meet their nutritional requirements. Catheter lock solution will be resumed based on the types of solution the patient is receiving at that point in time whenever a central catheter is present.

Compliance with catheter locks solution

Subject compliance will be checked when they will receive a phone call every months as a follow-up asking about the number of catheter lock solution used and the amount of solution infused. In addition, they will be asked if they have taken the TPN as per the instructions provided to them about the infusion.

SAFETY EVALUATION:

All AEs will be reported and evaluated. The research team will be responsible for detecting and documenting any AE or serious adverse event (SAE). This will help in identifying any untoward medical occurrence, thereby allowing the continuous safety of study subject and provide a greater understanding of the overall safety profile of the investigational product.

Adverse event Definition

An AE is defined as any untoward medical occurrence in a clinical investigation subject administered medical/ pharmaceutical product. An adverse event does not necessarily have to have a causal relationship with the medical/ pharmaceutical product.

An AE can therefore be any unfavorable and unintended sign (including a clinical significant abnormal laboratory finding), symptom, or disease temporally associated with the use of a medicinal product (investigational or marketed), whether or not considered related to treatment with the medicinal product.

An AE includes:

- An exacerbation of a pre existing illness, sign, symptom, or clinical significant laboratory test abnormality as determined by the investigator.
- An illness, sign, symptom, or clinically significant laboratory abnormality that is detected or diagnosed after study drug administration.
- Pre or post treatment events that occur as a result of protocol mandated procedures

An AE does not include:

- Expected worsening of the disease or disorder being studied or signs and symptoms associated with the disease or disorder
- A preexisting disease or condition, present at the start of the study that did not worsen
- Any overdose of the study drug or concurrent medication without any clinical sign or symptom.

Procedure for reporting adverse events

Any sign (e.g., a clinically significant abnormal laboratory finding, as determined by the investigator), symptom or disease described by the subject or noted by the research team will be recorded as an AE. If known, the diagnosis of the underlying illness or disorder will be recorded rather than its individual symptoms.

At each phone call, new AEs will be recorded on the CRF. The AE term should note the diagnosis of the event, not the individual signs of symptoms (e.g., sneezing, coughing recoded as upper respiratory tract infection).

Also, recorded are

- Start and stop date and time
- frequency (intermittent, continuous)
- Intensity (mild, moderate, severe)
 - Mild: usually transient, requiring no special treatment and generally not interfering with usual daily activities
 - Moderate: usually ameliorated by simple therapeutic maneuvers and impairs usual activities.
 - Severe: requires vigorous therapeutic intervention and or interrupts usual activities. Hospitalization may or may not be required.
- Relationship to study drug (not related, related). An event related to drug treatment, i.e., associated with drug treatment, is considered an adverse drug reaction (ADR). The term related includes unlikely (improbable), possibly, probably, and definitely.
- Whether or not the AE is serious (i.e., an SAE). If identified as an SAE, the AE should be reported on the SAE form and reporting guidelines followed.
- Actions taken (none; study drug dose interrupted or discontinued, other medication change, non drug therapy)
- Outcome (resolved, ongoing, fatal). If the AE has increased in severity or frequency, it should be identified as a new AE and given a new number

AE not resolved at the end of treatment will be followed for up to 4 weeks after the last dose of catheter lock solution or as long as judged medically relevant by the investigator.

Serious Adverse Events

An event that is serious must be recorded on the SAE report form and requires expeditious handling to comply with regulatory requirements.

Serious Adverse Event Definition

An adverse event is considered serious if it

- Occurs during study treatment or within 30 days of last dose of study drug (or after 30 days if considered to be a result of delayed toxicity due to administrations of study drug) and meets any of the criteria outlined below.

An SAE is any AE occurring at any dose that results in any of the following outcomes

- Death
- life threatening. A life threatening AE is any AE that place the subject in the investigator's opinion at immediate risk of death from the reaction as it occurred. It does not include a reaction that, had it occurred in a more serious form, might have caused death.
- Persistent or significant disability or incapacity
- Hospitalization or prolongation of existing hospitalization
- Congenital anomaly/ birth defect
- Important medical events that may not result in death, be life threatening, or require hospitalization may be considered an SAE when, based upon appropriate medical judgment, they may jeopardize the subject or may require medical or surgical intervention to prevent 1 of the other outcome listed in this definition.

Data storage:

All data regarding the study will be stored in hospital file and UHN computer system of the clinical fellow, nurse coordinator and principal investigator for 10 years.

Statistical analysis:

Simple statistics such as mean, median and frequency will be used to initially assess the data as follows:

1. Patient acceptability will be analyzed as the proportion of participants willing to continue use of the catheter lock solution. The solution will be deemed acceptable if at least 75% of participants are willing to continue use of the solution.

2. Patient satisfaction will be analyzed as the proportion of participants overall satisfied with the catheter lock solution.

3. Ease of use will be analyzed as the proportion of participants answering that the process is easy or very easy. This will be calculated by taking the average of the answers to the 3-5 questions at the top of the questionnaire addressing the ease of the procedure (preparation of the solution, instilling, withdrawing etc). Each step will also be analyzed individually (averaged over all of the patients), to determine if one of these individual averages falls below 3 (suggesting that that procedure is difficult).

The means of patient acceptability, patient satisfaction and ease of use of the new catheter lock solution flush and the new catheter lock solution withdraw will each be compared, separately, to those of the heparin group and to each other using the chi squared test to determine if there is any difference between them.

Sample Size and Feasibility

This is a pilot study; we plan to recruit 20 participants.

Limitations:

- The expected sample size is 20 subjects and some of them live far away from TGH. This can be avoided a phone call follow-up every month.
- Some of the patients may not be compliant with the catheter lock solution or TPN infusion. Compliance will be checked by counting the number of catheter lock solutions and tpn bags delivered and used. However, compliance cannot be predicted.

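### EDTA with withdrawal always falls in month 2 and flush-through always in month 3, so the planned test between them cannot separate technique from period

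*Protocol*

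**What the plan says.** The Research Design and Methods section of the protocol sets a single sequence for all participants. Month 1: "Patients will then start with one month (30 days) of their usual heparin and saline flush". Months 2 and 3: "one month (30 days) of tetrasodium EDTA solution with withdrawal (when possible), followed by one month (30 days) of tetrasodium EDTA solution". That sentence does not name the month 3 technique, but the Lock procedures section lists the third procedure as "Tetrasodium EDTA lock and flush through". The instructions then define the difference between the two EDTA techniques: "If flushing Tetrasodium EDTA lock solution through the catheter, repeat above steps but omit 5 - 7". Steps 5 to 7 are attaching the empty syringe, drawing back the lock solution and swabbing again. No second sequence, randomised order or concurrent control is described.

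The Statistical analysis section says that acceptability, satisfaction and ease of use of the flush and withdraw techniques "will each be compared, separately, to those of the heparin group and to each other using the chi squared test", in order to establish whether they differ. The ratings come from a survey at the end of each month.

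The Limitations section covers sample size and distance, compliance, and dropout. It does not mention order or period.

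**The concern.** When every participant uses technique A in one month and technique B in the next, a change in ratings between those months has at least two possible sources: the technique, and whatever else changed with time. Practice is the obvious candidate. The HPN administration section says that the new solution alters the patients' routine and calls for extra training because it is prepared from a vial. Month 2 is the first study month on EDTA; month 3 follows 30 days of handling it.

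A significant result would naturally be read as one technique being more acceptable, more satisfying or easier, when it could reflect period alone. A null result is no clearer, because technique and period effects could cancel. The risk is a wrong conclusion about which way of using the product patients prefer.

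**Working it through.** The protocol gives no significance level, effect size or derivation of its sample size, so there is no stated figure to reproduce. Two checks were made.

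**1. Can the two effects be separated?** Let μ be the heparin (month 1) mean, W and F the effects of withdrawal and flush-through relative to heparin, and π2 and π3 the effects of months 2 and 3 relative to month 1. The three monthly means are:

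- month 1: μ
- month 2: μ + W + π2
- month 3: μ + F + π3

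Month 3 minus month 2 = (F − W) + (π3 − π2). There are three means for five parameters, and the design matrix has rank 3. Only the sum of the two brackets can be estimated, so any period shift enters the estimated technique difference one for one. This follows from the design and needs no assumed number.

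**2. How often would a pure period shift be declared a difference?**

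Input from the protocol: n = 20 (Sample size section). Assumed inputs: F − W = 0; 60% positive in month 2; 60%, 70%, 80% or 90% positive in month 3; within-person correlation r of 0.3 to 0.5; two-sided 5% level (critical value 3.841); no dropout.

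Joint probability of a positive answer in both months: p11 = p2·p3 + r·√[p2(1−p2)·p3(1−p3)], where p2 and p3 are the month 2 and month 3 proportions. Example, 60% to 80% with r = 0.3: 0.48 + 0.3 × √(0.24 × 0.16) = 0.48 + 0.3 × 0.196 = 0.539. The other three cells follow from the margins. For 60% to 90%, r cannot exceed (0.60 − 0.54)/√(0.24 × 0.09) = 0.06/0.147 = 0.41.

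All paired outcomes for 20 people were enumerated exactly, and Pearson's chi-squared was applied as if to 20 versus 20 independent answers. The probabilities of a significant result are:

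| Month 2 → month 3 | Uncorrected, r = 0.3 | Uncorrected, r = 0.5 | Corrected, r = 0.3 | Corrected, r = 0.5 |
|---|---|---|---|---|
| 60% → 60% | 1.9% | 0.6% | 0.6% | 0.1% |
| 60% → 70% | 6.3% | 3.7% | 2.4% | 1.1% |
| 60% → 80% | 25.1% | 21.2% | 13.2% | 9.6% |
| 60% → 90% | 64.2% | 64.9% (r = 0.41) | 46.0% | 44.9% (r = 0.41) |

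In counts, with 12/20 positive in month 2, χ² = 40(ad − bc)²/(20 × 20 × row totals):

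- 17/20 in month 3: 40 × (12×3 − 8×17)²/(400 × 29 × 11) = 400,000/127,600 = 3.13, not significant.
- 18/20 in month 3: 40 × (12×2 − 8×18)²/(400 × 30 × 10) = 576,000/120,000 = 4.80, significant without continuity correction. With it, 40 × (120 − 20)²/120,000 = 3.33, not significant.

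**Would a paired test cure it?** No. In 20,000 simulated trials with the same fixed order and a pure 60% to 90% shift, the exact McNemar test rejected in 44% (latent correlation 0) to 51% (0.5). Pairing deals with the dependence between answers, not with the confounding.

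**The case against.** The strongest reply is that this contrast is peripheral. Comparing the two techniques is neither the primary objective nor a listed secondary aim; it appears in one clause of a self-described pilot of 20 patients. That is right, and it limits the weight of the point.

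The harm also depends on a period effect that the documents do not give. With five or more infusions a week, patients will have done about 20 EDTA locks before the month 2 rating (5 × 30/7 ≈ 21), so most of the learning may be over. Starting from 75%, the one proportion that the protocol states, a 10-point shift gives only 5.3–8.1% rejection and a 15-point shift 16–19% (uncorrected, r = 0.3 to 0.5). This also stands: the 20–30 point cases show what could happen, not what is expected.

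The protocol does hold partial information on practice. The techniques differ only at connection, so preparing the solution, instilling it and the separately timed phase "From disconnecting TPN tubing to completing catheter lock solution" are the same in both EDTA months. Times are also taken on the first and last Monday of each 30-day period, which shows a trend within a month under one technique. These data help to judge practice but do not separate the effects for acceptability, satisfaction or overall ease.

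Finally, both comparisons with heparin, always month 1, share the flaw. Month 2 withdrawal is done only when possible, and dropouts are not replaced, so the month 3 respondents may be a selected group. These points add to the ambiguity of the planned tests; none removes it.

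**Conclusion.** The concern holds. For the summary ratings, technique and month are completely aliased between the two EDTA months, and nothing in the protocol resolves this. The planned chi-squared test can show that months 2 and 3 differ; it cannot show that the techniques differ. That conclusion rests on the design alone.

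The practical size is uncertain because the size and direction of any period shift are unknown. Under the assumptions above, a 10-point shift barely moves the rejection rate from nominal, a 20-point shift gives roughly one false attribution in four or five trials, and a 30-point shift nearly two in three. The continuity-corrected rates are lower: 1–2%, 10–13% and 45–46%.

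The primary criterion, at least 75% willing to continue, does not need this contrast and is unaffected. The change should be made, but it concerns a secondary comparison.

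**What to change.** In the Statistical analysis section, remove the chi-squared test of withdraw against flush-through. Report the contrast descriptively as paired within-patient changes, with the numbers moving each way, and state that it is confounded with order. Beside it, show the month 2 to month 3 change in what both months share (the preparation item, the instilling item and the disconnect-to-lock time), together with the first-to-last-Monday change in time within each EDTA month, as a partial gauge of practice. Add fixed order to the Limitations section, and note there that the heparin comparisons carry the same confounding.

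The cost is wording in two sections and the p-values of one secondary contrast. All the data are already planned; no patients or visits are added.

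Whether both orders of the two EDTA months are clinically acceptable is for the sponsor. Only if the sponsor independently judges that they are could the order be randomised and period included in the comparison, assuming no unequal carry-over. In simulation with 10 patients per order and a pure 60% to 90% period shift, the mean technique difference was then 0.00 instead of 0.30, and the chi-squared test rejected in 2.0–3.8% of trials instead of 63–64%. That option would cost a short randomisation list and two sets of instructions.

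### The lock-time clock starts at disconnection, but the procedure lists every locking step as coming before disconnection, so the EDTA vial draw-up could go untimed

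*Protocol*

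**What the plan says.** Measures, item 3, is named for the time taken to prepare the EDTA lock and sets two intervals. The first runs from beginning preparation for the infusion to starting it. The second is "2) From disconnecting TPN tubing to completing catheter lock solution (form 1". Under Data collection forms, times go on Form 1 on two Mondays, the first and the last, of each 30-day period, so the heparin month is timed as well as both EDTA months.

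The lock procedure has two step lists. The locking list is headed "Prior to disconnecting PN tubing (when infusion complete" and has seven numbered steps, none of which is the disconnection:

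- Step 4: "Swab end cap properly with alcohol swab before attaching any syringes. Open clamp".
- Step 5b, heparin: "Flush and lock catheter with pre-filled heparin syringe as per usual routine".
- Step 6a, EDTA: "Draw up 3 ml or 5 ml Tetrasodium EDTA solution in empty syringe. Set aside". Steps 6b and 6c are then the saline flush and the EDTA flush and lock.

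The other list, for the period before connecting, does number its event, as step 9: "Connect to PN tubing as per routine". For month 3 the Protocol adds: "If flushing Tetrasodium EDTA lock solution through the catheter, repeat above steps but omit 5 - 7".

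**The concern.** The start event of the second interval cannot be placed relative to step 6a. The heading puts disconnection after all the locking steps, whereas the interval needs it before the lock is completed. The two sections therefore conflict, and the resolution a user chooses decides whether the draw-up is timed.

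Heparin comes pre-filled, so the draw-up is the main extra work at locking. The Protocol itself, under HPN administration, gives preparation from a vial as one reason for additional training. If the draw-up happens before the clock starts, a measure named for preparation time leaves out most of the preparation. If Form 1 records only the start and end of each interval, no later analysis can restore the missing time. Different people may give the lock (nurse, patient or family member), so practice could also vary between records.

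**Working it through.** No figure in the Protocol bears on this. It gives no expected time, difference or standard deviation for the time measure, and 20 is a pilot number without a derivation. The check is therefore of step order, followed by a count of records.

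**1. Match the locking steps.** Step 6b (saline flush) corresponds to 5a, and 6c (flush and lock) to 5b. Step 6a has no heparin counterpart. Gathering differs slightly too: step 2 of the locking list begins "Gather: pre-filled 10 ml saline syringe; alcohol swabs; 3 ml or 5 ml empty syringe" and goes on to name the EDTA vial or the heparin syringe. Pre-filled heparin needs neither a vial nor an empty syringe. So 6a is the main task that EDTA adds at locking, but not strictly the only one.

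**2. Place the disconnection.**

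| Where disconnection falls | What the second interval times for EDTA |
|---|---|
| After step 7 (heading read literally) | Nothing: the lock is complete before the clock starts |
| Before step 4 (suggested by the step order) | 6a, 6b and 6c: draw-up included |
| After a draw-up done first and set aside | 6b and 6c: draw-up excluded |

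For heparin, the last two placements both cover 5a and 5b.

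**3. Ask whether the first interval recovers it.** It does not. The connection list has no draw-up step, and its gathering step names saline, swabs and an empty syringe but no vial.

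**4. Express the effect on recorded time.** Let d be the draw-up time, f the share of EDTA records in which the clock started before 6a, and r any difference in the remaining timed steps. Then

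recorded EDTA-minus-heparin difference = r + f × d.

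The Protocol gives no value for d, so these are assumptions, with r = 0:

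| d (assumed, min) | f = 0 | f = 0.5 | f = 1 |
|---|---|---|---|
| 0.5 | 0 | 0.25 | 0.5 |
| 1 | 0 | 0.5 | 1 |
| 3 | 0 | 1.5 | 3 |

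More records would not help, because f is not observed.

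**5. Count the records, at full completion.** 20 participants × 2 Mondays = 40 per month. Over 3 months: 3 × 40 = 120 records of the second interval. The heparin month supplies 40, with no draw-up at issue. The two EDTA months supply 2 × 40 = 80, which is the ceiling on affected records.

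**The case against.** The strongest reply is that the written order largely answers the question. The end cap is swabbed for a syringe and the clamp opened at step 4, and the draw-up follows at 6a, so a participant following the numbers would probably have the draw-up inside the clock. Form 1, to which both intervals are assigned, is not shown and is the natural place for clock instructions. Teaching by telephone, a patient demonstration and monthly calls of about 40 minutes offer chances to explain it. All of this stands, and it is why the point is small. It does not remove the conflict between the two sections, and none of the passages on teaching mentions the clock.

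A second reply is that the Protocol names no time contrast between solutions, and that a statistical analysis plan, not shown, may define one. That also stands. But the EDTA time is ambiguous even on its own, and an analysis plan cannot supply time that was never recorded.

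A third is that disconnection is a crisp, observable event shared by both solutions, while the start of preparation is softer and self-reported. This is a fair cost of the remedy. Stating on Form 1 where the draw-up falls relative to disconnection would also resolve the ambiguity, but if it were placed before disconnection the preparation would stay untimed.

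**Conclusion.** The conflict is real and the point is minor. Up to 80 of 120 planned records of the second interval could omit the draw-up. That ceiling requires all 20 participants to complete and every EDTA user to draw up before disconnecting. The actual share and the minutes lost cannot be derived from the Protocol.

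Three stronger readings are tempting but unsupported:

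- **That the interval cannot be measured at all.** This takes the heading literally, but the connection list sits under a similar heading and still contains its own event, so the heading is a loose guide to order.
- **That month 3 against month 1 would time nothing specific to EDTA.** Withdrawal steps 5 to 7 are indeed dropped in month 3. But the gathering of an empty syringe stays in the connection list, and the heparin reconnection steps are not written out, so an exact count of EDTA-only steps is not secure.
- **That the main results are at risk.** Only the secondary aim on preparation and injection time is touched. The Statistical analysis section specifies comparisons for acceptability, satisfaction and ease of use, which come from the questionnaire and not from this clock.

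**What to change.** Reconcile the lock procedure with Measures, item 3, on where disconnection falls, leaving every clinical step as it is. Define the second interval, in the Protocol and on Form 1 and identically in all three months, as running from the start of preparing the lock (before any vial draw-up) to completion of the lock. This parallels the first interval, which already starts at preparation.

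The cost is one line in Measures, the matching line on Form 1 and one clarifying line in the lock procedure, with no added visit, procedure or participant. The change needs to be in place before the first timed Monday of month 1, so that heparin and EDTA share one clock. The small downside is that set-up time common to both solutions is then included, which may add some variability.
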